5.1.2.4 Combination Expansion Arms (Parts D and E)

The purpose of the cohort expansion is to gather additional safety, tolerability, preliminary efficacy, PK, and PD information regarding BMS-986226 in combination with either nivolumab (Part D) or ipilimumab (Part E). Continuous evaluation of toxicity events in the cohort expansions will be performed throughout enrollment in the expansion cohorts. All participants treated with BMS-986226 in combination with either nivolumab or ipilimumab are recommended to receive premedications, as described in Section 7.1, in order to reduce the risk of infusion-related reactions. If, at any time, the aggregate rate of treatment-related toxicities meeting DLT criteria exceeds 33% across all participants treated the findings will be discussed and further enrollment will be interrupted. Depending on the nature and grade of the toxicity, and after assessing the risk/benefit ratio, a new dose for all cohorts may be initiated at a lower dose level.

The dose and schedule of BMS-986226 in Parts D and E will be determined based on all available safety, tolerability, efficacy, PK, and PD data from Parts A, B, and C. Parts D and E will be implemented following the revised protocol to define dose, schedule, and population.

Approximately 40 participants will be enrolled in each of Parts D and E. Safety, efficacy, PK, and PD data will be used to determine the precise patient population that will be enrolled in the expansion arms.

Participants with a response of unconfirmed progressive disease, stable disease, partial response, or complete response, at the end of a given cycle will continue to the next treatment cycle. Participants will be allowed to continue study treatment until the first occurrence of any of the following:

- Completion of the maximum number of cycles
- Confirmed progressive disease
- Clinical deterioration suggesting that no further benefit from treatment is likely
- Intolerability to therapy
- Participant meets the criteria for discontinuation of study treatment as shown in Section 8.2.

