- **Part D and Part E** are cohort expansion that consist of BMS-986226 in combination with either nivolumab (Part D) or ipilimumab (Part E). Continuous evaluation of toxicity events in the cohort expansions will be performed throughout enrollment in the expansion cohorts. If, at any time, the aggregate rate of treatment-related toxicities meeting DLT criteria exceeds 33% across all participants treated, the findings will be discussed and further enrollment will be interrupted. Depending on the nature and the grade of the toxicity, and after assessing the risk/benefit ratio, a new dose for all cohorts may be initiated at a lower dose level. The dose and schedule of BMS-986226 in Parts D and E will be determined based on all available safety, tolerability, efficacy, PK, and PD data from Parts A, B, and C. Parts D and E will enroll approximately 40 participants in each cohort. Safety, efficacy, PK, and PD data will be used to determine the precise patient population that will be enrolled in the expansion arms.
- Participants will be enrolled using the Interactive Response Technology (IRT) during the screening phase.
- For Parts A, scans will be collected centrally and may be reviewed by BICR at a later date or at any time during the study. For Parts B, C, D and E scans will be collected centrally to be reviewed in real time by BICR.

Number of Participants:

The number of participants for this study will be approximately 234. Up to approximately 34 of these participants may be treated with monotherapy (Preliminary Safety Cohorts and Part A); approximately 6 evaluable participants may be treated at each dose level for Parts B1 and C1; approximately 6-12 evaluable participants may be treated at each dose level for Parts B2 and C2; up to 6 additional evaluable participants may be treated in Parts B and/or C at a recommended BMS-986226 dose regimen for Parts D and/or E to better characterize the safety, PK, and PD profile; approximately 80 participants will be treated in combination expansion arms, Parts D and E.

Study Phases and Duration:

Screening: The screening phase will last for up to 28 days and take place prior to the first administration of study treatment for all parts. During the screening phase, the participant's initial eligibility will be established and written informed consent will be obtained. Tumor biopsies collected for all participants will be centrally evaluated for ICOS expression by

Approved v 5.0

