5.1.6 Data Monitoring Committee and Other External Committees

As this is an early stage, first-in-human study, a data monitoring committee will not be used.

BMS has developed a multi-layered process to ensure safety monitoring through close collaboration of study site investigators, the BMS study team, and the BMS Global Pharmacovigilance and Epidemiology (GPVE)-led Medical Surveillance Team. Study safety will be evaluated continuously in real time by representatives of BMS GPVE, who operate independently from the clinical team and monitor safety across all BMS protocols. AEs will be monitored continuously by the medical monitor(s) and GPVE. Safety, PK, and PD data are

reviewed during teleconferences between investigators and the BMS clinical team, which will be held regularly. The decision to escalate or expand the dose will be based on the aforementioned review with investigators.

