7.1 Treatments Administered

The selection and timing of dose for each participant are presented in Table 7.1-1.

Table 7.1-1:Selection and Timing of Dose per Part

Study Treatment	Dose Level	Frequency of Administration	Route of Administration	Infusion time (Minute)
Preliminary Safety (Cohorts and Part A			
BMS-986226	2, 8, 25, 80, 200, 400, 800 mg	Q4W	IV	30
Part B1				
Nivolumab	480 mg	Q4W		30
BMS-986226	3 Doses evaluated by BLRM-copula, PK/PD	Q12W	IV	30
Part B2				
Nivolumab	480 mg	Q4W	IV	30
BMS-986226	3 Doses evaluated by BLRM-copula, PK/PD	Q4W	IV	30
Part C1				
Ipilimumab	3 mg/kg ^a	Q4W		30
BMS-986226	3 Doses evaluated by BLRM-copula, PK/PD	Q12W	IV	30

Revised Protocol No.: 04 Date: 31-May-2019

Study Treatment	Dose Level	Frequency of Administration	Route of Administration	Infusion time (Minute)
Part C2				
Ipilimumab	3 mg/kg ^a	Q4W		30
BMS-986226	3 Doses evaluated by BLRM-copula, PK/PD	Q4W	IV	30
Part D				
Nivolumab	480 mg	Q4W	IV	30
BMS-986226	PK/PD from Part B	TBD	1 V	30
Part E				
Ipilimumab	3 mg/kg ^a	Q4W	IV	30
BMS-986226	PK/PD from Part C	TBD	IV	30

Table 7.1-1:Selection and Timing of Dose per Part

^a Weight collected at baseline/screening should be used to calculate ipilimumab dose unless weight has changes more than +/- 10% from baseline on C1D1

Note: In Parts B, C, D, and E a 30-minute infusion of either nivolumab or ipilimumab will be followed by a 30-minute observation period, followed by a 30-minute infusion of BMS-986226. In all parts, participants will be observed for at least 60 minutes following the completion of BMS-986226 infusion due to the potential risk of, and to monitor for, infusion reactions.

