7.3.2 BMS-986226 Dose-limiting Toxicities

For the purpose of guiding dose escalation, DLTs will be defined based on the incidence, intensity, and duration of AEs for which no clear alternative cause is identified. The DLT period will be 35 days (5 weeks).

In the Preliminary Safety Cohorts, participants who have received 1 dose of BMS-986226 and have completed, or who discontinued due to a DLT in the 4-week DLT period, will be considered as DLT-evaluable participants for BMS-986226 monotherapy.

In Part A, participants who have received 2 doses of BMS-986226 and have completed, or who discontinued due to a DLT in the 5-week DLT period, will be considered as DLT-evaluable participants for BMS-986226 monotherapy.

In Parts B, C, D and E, participants receiving either 1 dose of BMS-986226 or 2 doses of either nivolumab or ipilimumab, or participants who discontinued due to a DLT in the 5-week combination treatment DLT period, will be considered as DLT-evaluable participants for combination treatment. Participants who withdraw from the study during the DLT evaluation period or have received less than 2 doses for reasons other than a DLT in the monotherapy (Part A) or 1 dose in combination therapy (Parts B, C, D, E), will not be considered as DLT-evaluable participants in Part A, who are dose delayed during the DLT evaluation period for reasons other than a DLT could be considered as DLT-evaluable participants if they receive at least 2 doses of therapy.

For the purpose of participant management, any AE that meets DLT criteria, regardless of the cycle in which it occurs, will lead to discontinuation of study treatment (except as defined in Section 7.3.5). Participants who withdraw from the study during the 5-week DLT evaluation period for reasons other than a DLT may be replaced with a new participant at the same dose

level. The incidence of DLT(s) during the 5-week DLT evaluation period will be used in dose escalation decisions through application of the BLRM/BLRM-Copula model. AEs occurring after the DLT period will be considered to enhance the robustness of BLRM/BLRM-Copula prediction, upon agreement between the Sponsor, Medical Monitor/Study Director (or designee), and investigators.

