10.1.3 Combination Expansion Arms (Parts D and E)

Approximately 40 evaluable participants will be treated in each of Parts D and E. This sample size provides each cohort with about 87% probability to detect any AE with an event rate of 5%.

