10.2 Populations for Analyses

Population	Description
Enrolled	All participants who have signed an ICF and are registered into the IRT
Treated	All participants who received any dose of study treatment
Response-evaluable	All treated participants with measurable disease at baseline and 1 of the following: (1) at least 1 postbaseline tumor assessment, (2) clinical progression, or (3) death.
Pharmacokinetic	All treated participants who have evaluable concentration-time data.

For purposes of analysis, the following populations are defined:

Population	Description
Immunogenicity	All treated participants who have a baseline and at least 1 postbaseline immunogenicity measurement.

Abbreviations: ICF = informed consent form; IRT = Interactive Response Technology.

Analyses of safety, extent of exposure, **PK**, efficacy, and immunogenicity will be based on all treated participants.

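### The 33% toxicity trigger for the expansion phase most naturally pools Parts D and E, with no threshold per combination, so a high rate in one can be diluted by the other.

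*Combined protocol and SAP*

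**What the plan says.** The Synopsis and Section 5.1.2.4 give the same rule. Toxicity in the expansion cohorts is evaluated continuously. If at any time "the aggregate rate of treatment-related toxicities meeting DLT criteria exceeds 33% across all participants treated", the findings are discussed and further enrolment is interrupted. After a benefit-risk assessment, "a new dose for all cohorts may be initiated at a lower dose level". No part or combination is named, and no section adds a threshold for Part D or Part E alone.

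Other sections bear on how the rule is read:

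- Section 10.1.3 sizes D and E separately, about 40 each. Section 5.2 puts the two together at about 80 of 234 participants.
- Table 7.1-1 lists "PK/PD from Part C" as the basis for the BMS-986226 dose in Part E, and the corresponding Part B data for Part D. Section 5.1.2.4 itself says that dose and schedule use data from Parts A, B and C.
- Section 7.3.2 defines DLT-evaluable participants for Parts B to E and a 5-week DLT period. For participant management it also recognises "any AE that meets DLT criteria, regardless of the cycle in which it occurs".
- Section 5.1.6 provides no data monitoring committee. Safety is reviewed in real time by pharmacovigilance staff "who operate independently from the clinical team and monitor safety across all BMS protocols".
- Section 5.1.2.4 also says "Parts D and E will be implemented following the revised protocol to define dose, schedule, and population".

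**The concern.** Parts D and E give the same investigational antibody with two different partner drugs, and the purpose of expansion is to characterise each combination. With equal enrolment, an aggregate rate sits midway between the two parts' rates. If one combination is well tolerated, its participants offset events in the other, and the trigger may stay silent while one part is well above 33%. This is the only numerical enrolment trigger stated for these 80 participants.

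The terms of the rate are also loose. A rate of toxicities could count events or participants. It is not said whether events after the 5-week period count. Participants treated include those still inside their 5-week window, who enter the denominator before their outcome is known. No first look is given. Two teams could compute different rates from the same data.

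**Working it through.** **The plan's own figure.** The 87% in Section 10.1.3 for seeing an AE with a 5% event rate reproduces: 1 - 0.95^40 = 0.871. It is a per-part figure. The plan gives no operating characteristics for the 33% trigger.

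**Rule checked.** The pool fires when (x_D + x_E)/(n_D + n_E) > 0.33, and Part E alone when x_E/n_E > 0.33, where x counts participants with a qualifying event. With equal enrolment the expected pooled rate is (p_D + p_E)/2:

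- D 10%, E 45%: (0.10 + 0.45)/2 = 0.275, below 0.33.
- D 16%, E 35%: (0.16 + 0.35)/2 = 0.255, below 0.33.

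**Probability of firing, outcomes known at once.** Let f_n(k) be the probability of k events among n participants with no trigger so far. Then f_n(k) = f_{n-1}(k)(1 - p_n) + f_{n-1}(k-1)p_n where k/n ≤ 0.33, and 0 otherwise. The probability of firing is 1 minus the sum of the final f. For the pool, p_n alternates between the two parts over 80 participants; the ranges below cover which part enrols first.

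**With a lag.** The denominator is everyone treated so far. Event times are uniform over 5 weeks, with 40 participants per part at fixed intervals, at 0.5, 1 or 2 per part per week. This is a simulation with Monte Carlo error of about 0.01.

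| Assumed true rates and reading | D+E pool fires | Part E alone fires |
|---|---|---|
| D 10%, E 45%, known at once | 79-85% | 99% |
| Same, looks from n = 10 | 60-63% | 98% |
| D 10%, E 45%, treated denominator with lag, 0.5/1/2 per week | about 63/45/24% | 99/98/97% |
| D 16%, E 35%, known at once | 74-78% | 93% |
| D 16%, E 35%, treated denominator with lag | 58/38/18% | 91/86/77% |
| D 13%, E 18%, known at once | 45-48% | 54% |

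The n = 10 row counts 10 pooled participants for the pool and 10 Part E participants for E alone. Reading 33% as 1/3 gives 73-76% against 99% in place of the first row.

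**Is a wide gap plausible?** Appendix 10 gives related Grade 3-4 AEs, not DLTs, for the partner drugs at 3 mg/kg:

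- Nivolumab: 150/1146 = 13%.
- Ipilimumab: (27 + 16 + 66 + 10)/(131 + 111 + 362 + 71) = 119/675 = 18%.

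These do not support a 35-point difference. The last table row uses them; both parts are then below 33%, so every firing is a chance pause.

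**Would Part C have screened out a high rate?** The cut-offs here are illustrative. A true 45% yields at most 1 DLT in 6 with probability 0.55^6 + 6 × 0.45 × 0.55^5 = 0.16, and at most 3 in 12 with probability 0.13. At a true 35% the figures are 0.32 and 0.35. Screening helps but is incomplete.

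**Cost of splitting.** At a true 16%, one part of 40 fires with probability 0.48 and the pool of 80 also with 0.48. At least one of two parts fires with probability 1 - (1 - 0.48)^2 = 0.73. If looks start at n = 10, the figures are 26% for at least one part and 14% for the pool.

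**The case against.** Pooling over the shared investigational agent is a legitimate design, and the text leans that way: an aggregate rate, all participants treated, action for all cohorts. That stands as a reading, but the plan does not justify it, and one pooled number cannot represent two regimens whose rates differ.

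The trigger leads to discussion and a pause, and other protections exist. Combination safety is established first in Parts B and C. The overdose criterion of Appendix 10 applies to those parts, and Section 5.5.4 carries monotherapy toxicity forward into D and E. The study is open-label, Section 3.3 provides continuous review by investigators and sponsor, and Section 10.3 summarises by cohort. The data remain visible by part, so dilution means only that the numerical trigger may not fire. This lowers the consequence, but none of these is a per-part trigger.

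Early noise also matters. At a true 16%, one part fires within three participants with probability 1 - 0.84^3 = 0.41. Hence the first look needs stating in any case, and the n = 10 comparison is given above.

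Two stronger readings are tempting. A reader might infer from the Treated population in Section 10.2, "All participants who received any dose of study treatment", that the pool is the whole study. That population is defined for analysis, whereas the trigger follows a sentence about the expansion cohorts, so this reading is much weaker. A reader might also work out how high one part could go with both parts full and no trigger. By then no enrolment remains to interrupt, so it says little about this rule.

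**Conclusion.** The point holds as a cheap improvement to a safety rule. The trigger most naturally pools D and E, there is no threshold per combination, and dilution is material if the two rates differ widely. At assumed rates of 10% and 45%, the pool fires in 79-85% of trials against 99% for Part E alone, and less often still if everyone treated is the denominator. With E at 35%, just above the threshold, and D at 16%, it is 74-78% against 93%.

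The size depends on assumed rates, accrual, enrolment order and event timing. The documents do not show that such a gap is likely, nor that a high rate in one part would go unnoticed. Parts D and E cannot open under this version, so nobody is yet exposed to the wording.

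**What to change.** In the revision that Section 5.1.2.4 already requires:

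1. Apply the existing 33% enrolment trigger separately to Part D and to Part E. A pooled rate may be kept as an addition.
2. Count participants with at least one qualifying event, and say whether events after the 5-week period qualify.
3. Use the DLT-evaluable participants that Section 7.3.2 already defines for D and E. That definition can be met after one dose of BMS-986226, so also say how participants still inside the window are treated. Handle them even-handedly, for example by judging only those whose window has closed. Counting events at once but event-free participants only after 5 weeks would raise one part's chance pause at a true 16% from 0.48 to about 0.55/0.63/0.75 at 0.5/1/2 per week.
4. State the first look and whether 33% means 0.33 or 1/3, and tabulate trigger counts by n.

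The cost is wording, one table and more chance pauses. With window-closed looks, at least one part pauses in 73% of trials against 48% for the pool at a true 16% in both (26% against 14% from n = 10), and in 93% against 75% at a true 25%. Each pause then affects one part, and a given part's own chance is about unchanged (0.48 against 0.48 at 16%). Window-closed looks come somewhat later: with E at 45% and 1 per week, median Part E enrolment at the trigger is 7 rather than 5. The threshold value and any dose action stay with the sponsor.

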5.1.3 Follow-up

5.1.3.1 Safety Follow-up

Upon completion of 24 weeks of study treatment for Part A (or up to a maximum of 48 weeks if applicable) or 2 years for Parts B, C, D, and E, once the decision is made to discontinue the participant from study treatment (e.g., at end of treatment [EOT]), all participants will enter the safety follow-up period.

For participants who complete all scheduled cycles of therapy, the EOT visit will be the same as the last scheduled and completed on-treatment visit and the start of the Week 1 safety follow-up visit. For participants who do not complete all scheduled cycles of study treatment, the EOT visit will be the most recent on-treatment visit (with all available safety and response data), does not need to be repeated, and will be considered the start of the safety follow-up visit.

After the EOT visit, all participants will be evaluated for any new AEs for at least 100 days after the last dose of study treatment. Follow-up visits to monitor for AEs should occur at Days 30, 60, and 100 after the last dose or on the date of discontinuation (\pm 7 days). All participants will be required to complete the 3 clinical safety follow-up visits regardless of whether or not they start new anti-cancer treatment, except those participants who withdraw consent for study participation.

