- Part C2: Combination therapy will consist of BMS-986226 administered every 4 weeks (Q4W) + ipilimumab 3 mg/kg Q4W for up to 2 years of treatment. Following each treatment cycle, the decision to treat a participant with additional cycles of study treatment, will be based on safety, tolerability, and tumor assessments performed every 8 weeks (± 1 week).

The treatment phase in the Preliminary Safety Cohort and Part A consists of up to six 4-week treatment cycles (1 cycle = 28 days). In the Preliminary Safety Cohort and Part A, each treatment cycle will consist of BMS-986226 monotherapy for a total of 24 weeks.

In Parts B1 and C1, 4 week cycles will be used, such that BMS-986226 + nivolumab or ipilimumab will be administered starting on Cycle 1 Day 1. Nivolumab and ipilimumab will be administered on Day 1 of each cycle. BMS-986226 will be administered Q12W, or on Day 1 of every third cycle

(Cycle 1 Day1, Cycle 4, Day1, Cycle 7 Day1, etc.). Participants on Parts B1 and C1 may continue treatment for up to a total of 2 years.

The treatment phase in Parts B2 and C2 will consist of BMS-986226 + nivolumab or ipilimumab administered on Day 1 of each cycle for up to a total of 2 years. Participants in Parts B2 and C2 will be enrolled if additional safety, PK, or PD data is required to optimize dose and/or schedule selection.

Follow-up: Safety follow-up will occur 30, 60, and 100 days (\pm 7 days) after either the last dose or the date of discontinuation. All participants treated with monotherapy or combination therapy will enter the survival follow-up period after the last safety visit. All participants treated with monotherapy or combination therapy with ongoing stable disease (SD), partial response (PR), or complete response (CR) will enter the response follow-up period after the last safety visit. If the participant discontinues treatment for any reason other than PD, radiological follow-up will continue until the participant receives additional treatment.

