Monitor for Non-serious AEs		Х								Non-serious AEs will be collected starting with the first dose of study treatment and through 100 days after last dose of study drug, or until new anti-cancer treatment is initiated, whichever comes first.
Monitor for SAEs					Х					See note in Table 2-1.

Procedures for Safety Cohort, and Parts A, B, C, D and E ^{a,b}				C2 to beyond	C2 Only	C2 Only		Notes		
Procedure	D1	D2	D8 ± 1 days	D15 ± 1 days	D22 ± 1 days	D1	D2	D8 ± 1 days	EOT c,d,e	
Sample Collection										
PK Assessments			See Ta	ble 9.5-1,	Table 9.5	9.5-4	See Section 9.5. To be performed in all participants.			
Immunogenicity Assessments			See Ta	ble 9.5-1,	Table 9.5	5-2, Table 9	9.5-4.			

Procedures for Safety Cohort, and Parts A, B, C, D and E ^{a,b}			C1			C2 to beyond	C2 Only	C2 Only		Notes	
Procedure	D1	D2	D8 ± 1 days	D15 ±1 days	D22 ± 1 days	D1	D2	D8 ±1 days	EOT c,d,e		
Efficacy Assessments											
Body Imaging						Every 8 weeks (± 1 week) prior to dosing at C3 and C5			X	See Section 9.1.	
Brain Imaging					per standa	y of brain n ard of care f illy indicate	See Section 9.1.				
Bone Scan					As clini	cally indica	ted.			See Table 2-1. See Section 9.1.	
Study Treatment Adminis	stration	Details regarding preparation and administration are provided in site training materials. In all study parts, participants will be observed for at least 60 minutes following the completion of BMS-986226 infusion due to the potential risk of, and to monitor for, infusion reactions.									

Procedures for Safety Cohort, and Parts A, B, C, D and E ^{a,b}			C1			C2 to beyond	C2 Only	C2 Only		Notes
Procedure	D1	D2	D8 ± 1 days	D15 ± 1 days	D22 ± 1 days	D1	D2	D8 ±1 days	EOT c,d,e	
All Parts: Premedication	Х					Х				In all study parts, participants are recommended to receive premedication 30 minutes prior to infusion of any study drug, to reduce the risk of infusion-related reactions, as described in Section 7.1 and Section 7.3.6. Any modification to the recommended regimen must be discussed and agreed upon with BMS Medical Monitor/Study Director.

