All Parts: BMS-986226 Administration	Х					Х				Use vials assigned per IRT. Safety Cohort and Part A BMS-986226 will be administered every 4 weeks on the first day of each cycle Parts B1 and C1: BMS-986226 will be administered on Day 1 every 12 weeks (Cycle 1 Day1, Cycle 4 Day1, Cycle 7 Day 1, etc) Parts B2 and C2: BMS-986226 will be administered every 4 weeks on the first day of each cycle Parts D and E: The dose and schedule of BMS-986226 will be determined based on available data from Parts A, B1, B2, C1 and C2.

Procedures for Safety Cohort, and Parts A, B, C, D and E ^{a,b}			C2 to beyond	C2 Only	C2 Only		Notes			
Procedure	D1	D2	D8 ± 1 days	D15 ±1 days	D22 ±1 days	D1	D2	D8 ±1 days	EOT c,d,e	
Parts B1, B2, and D ONLY: Nivolumab Administration	Х					Х				Use vials assigned per IRT. Nivolumab is administered ONLY for those participants enrolled in Parts B1, B2, and D.
Parts C1, C2, and E ONLY: Ipilimumab Administration	Х					X				Use vials assigned per IRT. Ipilimumab is administered ONLY for those participants enrolled in Parts C1, C2 and E.

^a The procedural outline for participants who receive additional cycles are outlined in Table 2-4.

^b Participants taking 2 or 8 mg of BMS-986226 in the Preliminary Safety Cohorts will follow the same procedure schedule as in Part A. In the event that participants taking 2 or 8 mg of BMS-986226 should be permitted to intra-dose escalate up to 8 and/or 25 mg, the sampling schedule should be restarted at Cycle 1 Day 1 at each dose escalation, and an additional tumor biopsy may be optionally re-collected at C1D15.

^c EOT is defined as the visit where a decision is made to discontinue the participant from treatment.

^d For participants who complete all scheduled cycles of therapy, the EOT visit will be the same as the last scheduled and completed on-treatment visit (eg, Cycle 6 Day 175) and the start of the Week 1 safety follow-up visit.

^e For participants who do not complete all scheduled cycles of therapy, the EOT visit will be the most recent on-treatment visit (with all available safety and response data) and does not need to be repeated, and it will be considered the start of the Week 1 safety follow-up visit.

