Abbreviations: AE = adverse event; C1 = Cycle 1; C2 = Cycle 2; C3 = Cycle 3; C5 = Cycle 5; C6 = Cycle 6; CBC = complete blood count; ; ECOG = Eastern Cooperative Oncology Group; EOT = end of treatment; D1 = Day 1; D2 = Day 2; D4 = Day 4; D8 = Day 8; D15 = Day 15; D21 = Day 21; hCG = human chorionic gonadotropin; IRT = Interactive Response Technology; PE = physical examination; PK = pharmacokinetic; PD = pharmacodynamic; Q12W = every 12 weeks; RECIST v1.1 = Response Evaluation Criteria in Solid Tumors Version 1.1; T3 = triiodothyronine; T4 = thyroxine; TSH = thyroid-stimulating hormone; WOCBP = women of childbearing potential.

	S	afety Follow-u	p ^a	Survival/Response Long-term Follow-up	
Procedure	FU 1 30 days (± 7 days)	FU 2 60 days (± 7 days)	FU 3 100 days (± 7 days)	Begins After Completion of Safety Follow-up Q12W (Q12W ± 2 weeks) Until 2 Years After Last Dose of Study Treatment	Notes
Safety Assessments					
Symptom-directed PE	X	Х	Х		Symptom-directed only.
ECOG Performance Status	X	Х	Х		ECOG score (Appendix 7)
Vital Signs	X	Х	Х		See note in Table 2-1.
Laboratory Tests					See note in Table 2-1.
Chemistry	X	Х	X		See note in Table 2-1.
CBC with Differential and Platelets	X	Х	X		See note in Table 2-2.
Thyroid Function Tests	X	Х	Х		See note in Table 2-2.
Urinalysis	As clinically indicated.			See Section 9.4.4. See note in Table 2-1.	
Pregnancy Test	Х	Х	X		See note in Table 2-2.
AE Reporting					
Concomitant Medication Assessments	X	Х	X		
Monitor for Non-serious AEs	X	Х	X		See note in Table 2-2.
Monitor for SAEs	X	Х	Х		See note in Table 2-1.
Sample Collection	Sample Collection				
PK Assessments	See Table 9.5-1, Table 9.5-2, Table 9.5- 3, and Table 9.5-4			See Section 9.5.	

Table 2-3:Follow-up Procedural Outline (CA021002)

Table 2-3:	Follow-up Pi	rocedural Outli	ne (CA021002)
------------	--------------	-----------------	---------------

	Safety Follow-up ^a			Survival/Response Long-term Follow-up	
Procedure	FU 1 30 days (± 7 days)	FU 2 60 days (± 7 days)	FU 3 100 days (± 7 days)	Begins After Completion of Safety Follow-up Q12W (Q12W ± 2 weeks) Until 2 Years After Last Dose of Study Treatment	Notes
Immunogenicity (eg, ADA) Assessments		L	1		
Efficacy Assessments					
Body Imaging			X	x ^b	See Section 9.1. Participants should undergo tumor assessment via CT/MRI scans at least Q12W during the survival follow-up period until beginning a new anti-cancer therapy.

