9.2.1 Time Period and Frequency for Collecting AE and SAE Information

The collection of non-serious AE information should begin at the initiation of study treatment until 100 days of the last dose of study treatment, at the time points specified in the Schedule of Activities (Section 2).

Following the participant's written consent to participate in the study, all SAEs, whether related or not related to study treatment, must be collected, including those thought to be associated with protocol-specified procedures.

All SAEs that occur during the screening period and within 100 days of the last dose of study treatment must be collected. If applicable, SAEs that relate to any later protocol-specified procedure (eg, a follow-up skin biopsy) must be collected. For participants assigned to treatment and never treated with study treatment, SAEs should be collected for 30 days from the date of treatment assignment.

The investigator must report any SAE that occurs after these time periods and that is believed to be related to study treatment or protocol-specified procedure.

- Medical occurrences that begin before the start of study treatment but after obtaining informed consent will be recorded on the appropriate section of the CRF section.
- All SAEs will be recorded and reported to the Sponsor or designee within 24 hours, as indicated in Appendix 3.
- The investigator will submit any updated SAE data to the Sponsor within 24 hours of this being available.

An SAE report should be completed for any event where doubt exists regarding its seriousness.

If the investigator believes that an SAE is not related to study treatment, but is potentially related to the conditions of the study (such as withdrawal of previous therapy or a complication of a study procedure), the relationship should be specified in the narrative section of the SAE Report Form.

Investigators are not obligated to actively seek AEs or SAEs in former study participants. However, if the investigator learns of any SAE, including a death, at any time after a participant has been discharged from the study, and he/she considers the event reasonably related to the study treatment or study participation, the investigator must promptly notify the Sponsor.

The method of evaluating and assessing causality of AEs and SAEs and the procedures for completing and reporting/transmitting SAE reports are provided in Appendix 3.

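### FU 3 may fall on Day 93 after the last dose with no later scheduled AE assessment, so the required 100 days of AE evaluation are not guaranteed

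*Combined protocol and SAP*

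**What the plan says.** Section 5.1.3.1 sets a minimum period: "all participants will be evaluated for any new AEs for at least 100 days after the last dose of study treatment". It then sets the visits, with a tolerance of 7 days either way: "Follow-up visits to monitor for AEs should occur at Days 30, 60, and 100 after the last dose or on the date of discontinuation". Table 2-3 has a column "FU 3 100 days (± 7 days", and Table 2-5 repeats that window. The synopsis gives the same days and tolerance, counted "after either the last dose or the date of discontinuation".

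The collection periods also run to Day 100:

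- **Non-serious AEs** (note in Table 2-2): "Non-serious AEs will be collected starting with the first dose of study treatment and through 100 days after last dose of study drug". Collection stops sooner if another anti-cancer treatment is started. Section 9.2.1 ties this collection to the time points in the Schedule of Activities.
- **SAEs** (Section 9.2.1): "All SAEs that occur during the screening period and within 100 days of the last dose of study treatment must be collected". No visit date is mentioned.

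Table 2-3 marks AE and SAE monitoring at FU 1, FU 2 and FU 3 only. The long-term column, with contacts every 12 weeks, covers imaging, survival status and new anti-cancer therapy. Incidence of AEs and SAEs is part of the primary endpoint (Table 4-1).

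**The concern.** A minimum of 100 days and a closing visit allowed from Day 93 do not fit together. If FU 3 is timed from the last dose and held in the early half of its window, the site has followed the schedule, yet the participant has not been evaluated for 100 days. The next scheduled contact is about 12 weeks later and carries no AE item.

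A non-serious AE that begins between an early FU 3 and Day 100 belongs in the primary endpoint, but no scheduled assessment would find it. Any such loss can only lower the count. Its extent depends on how sites book the visit, and on which of the two permitted anchors they use.

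**Working it through.** **1. The plan's own figures.** The nearest stated quantity is the probability of seeing at least one AE of a given rate, P = 1 − (1 − p)^n.

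- Parts D and E (Section 10.1.3), n = 40, p = 0.05: 1 − 0.95^40 = 87.1%; stated as about 87%.
- Parts B1 and C1 (Section 10.1.2), n = 6, p = 0.24: 80.7%; stated as about 80%.
- Parts B2 and C2 (Section 10.1.2), n = 12, p = 0.24: 96.3%; stated as up to 96%.

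All three reproduce.

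**2. The window.** 100 − 7 = 93 and 100 + 7 = 107, so there are 15 permitted days, of which 7 (Days 93 to 99) precede Day 100.

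**3. Share seen early.** The documents give no distribution of visit dates, so the window alone permits 0% to 100%. As an illustration, assume visits uniform over the 15 days, counted from a date g days after the last dose. The share before Day 100 is max(0, 7 − g)/15.

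| g (days) | Earliest FU 3, days after last dose | Share before Day 100 |
|---|---|---|
| 0 | 93 | 7/15 = 46.7% |
| 3 | 96 | 4/15 = 26.7% |
| 7 | 100 | 0% |
| 28 | 121 | 0% |

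**4. Days lost, at g = 0 and uniform visits.** Among those seen early: (1 + 2 + … + 7)/7 = 4.0 days. Over all participants: 28/15 = 1.9 days.

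**5. Effect on the stated 87%.** Assume a constant AE hazard, a 5% risk over the whole observation period, and nothing captured after FU 3. If a fraction f of the period is observed, P = 1 − 0.95^(40f).

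- Worst case: period of 100 days only, everyone loses 7 days, f = 0.93: 85.2%.
- Period of 24 weeks + 100 days = 268 days, everyone loses 7, f = 261/268: 86.4%.
- Period of 2 years + 100 days = 830 days, everyone loses 7, f = 823/830: 86.9%.
- Period of 100 days, uniform visits, f = 1 − (28/15)/100 = 0.981: 86.6%.

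The same worst case (f = 0.93) takes 80.7% to 78.4% for n = 6 and 96.3% to 95.3% for n = 12.

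**The case against.** The strongest reply is that collection does not stop at the visit. For SAEs this stands: Section 9.2.1 requires every SAE within 100 days of the last dose to be collected, and later related ones to be reported. For non-serious AEs it stands only in part, because their collection is tied to scheduled time points and FU 3 is the last of these.

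The second reply is the alternative anchor, and it also stands. Visits may be tied to discontinuation, and "EOT is defined as the visit where a decision is made to discontinue the participant from treatment", which can be well after the last dose. The footnotes give Cycle 6 Day 175 as a completer's end-of-treatment visit. Read as study Day 175, with Cycle 6 Day 1 at 5 × 28 + 1 = 141, that is 34 days after the last dose. An FU 3 counted from it could not precede Day 34 + 93 = 127. Participants who stop early may have no such gap.

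Four stronger readings are tempting but not supported:

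- A reader might infer that about half of participants, or 7/15 × 234 = 109 people, have their last AE visit early. That needs uniform visits, the last-dose anchor for everyone, and all 234 reaching FU 3. Death, withdrawal and loss reduce the number, and new anti-cancer treatment ends the non-serious AE period sooner. Nor is half an upper bound.
- A reader might extend the gap to laboratory abnormalities. Section 10.3.2 analyses the worst grade on treatment, and no section sets a 100-day laboratory period.
- A reader might take "Investigators are not obligated to actively seek AEs or SAEs in former study participants" as closing AE enquiry after FU 3. That paragraph of Section 9.2.1 concerns people discharged from the study; these participants are entering survival follow-up.
- A reader might see a biased comparison between cohorts. The synopsis says no prospective hypothesis is formally evaluated, so no planned test is affected.

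**Conclusion.** The inconsistency is real and minor. With the last-dose anchor, a compliant FU 3 can leave up to 7 of the 100 days without a later scheduled AE assessment, so the minimum in Section 5.1.3.1 is not assured. The exposure is mainly new non-serious AEs.

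How many participants are affected cannot be determined from the documents, because it depends on visit dates and on the anchor each site uses. The direction is under-counting. The size is at most about 2 points on the stated 87%, and that figure rests on the worst case: constant hazard, a period of only 100 days, every participant seen on Day 93, and nothing recorded afterwards. Under the longer observation periods, or with uniform visits, the change is below 1 point.

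**What to change.** Set FU 3 to 100 days (+ 7 days) after the last dose. Make the change in the synopsis follow-up paragraph, in Tables 2-3 and 2-5 including the footnotes that allow either anchor, and in Section 5.1.3.1; leaving out any one of these would create a new contradiction. FU 3 then cannot precede Day 100 after the last dose, whichever anchor is used for FU 1 and FU 2, and both can keep ± 7 days.

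No visit is added. The cost is wording in those places and a window of 8 days (100 to 107) instead of 15 for one visit. The amendment should also state the anchor for FU 1 and FU 2. With a 34-day gap, for example, an FU 2 counted from discontinuation falls nominally on Day 34 + 60 = 94 after the last dose, close to FU 3.
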